## 4.4. Radiotherapy in standard risk medulloblastoma.

#### 4.4.1 Rationale for dose reduction.

Until recently, the standard therapeutic approach for standard risk medulloblastoma has consisted of complete or near complete surgical resection followed by post-operative CSRT. The conventional doses of radiotherapy are around 36 Gy to the craniospinal axis together with a boost of 18 to 20 Gy to the posterior fossa (total dose 54 to 56 Gy). Using such doses, various studies have reported that between 55 and 70% of children are alive and free of progressive disease five years from diagnosis 10 11.

It is now clear that a high proportion of survivors of medulloblastoma have significant long-term sequelae. Although some of these late effects are related to the tumour itself, hydrocephalus and the complications of both surgery and chemotherapy, it is probable that the most important factor in the pathogenesis of these significant sequelae is the dose of CSRT needed to treat this disease. Of most concern are the well-recognised neuropsychological sequelae of children receiving cranial irradiation. Several studies have demonstrated marked losses of IQ of up to 30 points or more which are most predominant in young children, particularly those less than seven or eight years of age. Several workers investigating these effects have compared the effects of CSRT for the treatment of medulloblastoma with posterior fossa radiotherapy alone e.g. for tumours such as cerebellar astrocytoma and ependymoma . Such studies have clearly shown the marked deleterious effects of whole brain radiotherapy  .

In addition, it is clear that the majority of survivors suffer significant growth and endocrine dysfunction predominately due to irradiation of the pituitary gland and hypothalamic regions together with the effects of whole spine radiotherapy 15 16 17. Although exact dose effect relationships are not known, there is evidence to suggest that dose reduction might decrease the risk for such hypothalamic-pituitary dysfunctions as well as for decreasing the risk for growth retardation of the spine. Moreover, radiotherapy of the spinal canal may be responsible for thyroid dysfunction, and also gonadal dysfunction in young girls caused by scattered irradiation.

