Several, often small, studies do appear to show a dose effect relationship between 24 and 36 Gy to the brain 18 19 20 although such studies usually contain small numbers and/or a heterogeneous population in terms of disease and treatment. In a recent study, Grill et al showed there is a significant correlation between the full-scale IQ score (FSIQ) and the CSRT dose, with mean FSIQ scores at 84.5, 76.9 and 63.7 for 0 Gy (i.e. posterior fossa radiotherapy alone), 25 Gy and 35 Gy of CSRT respectively 21. An analysis of the neuropsychological sequelae reported in the literature 22 has been used to construct a dose response curve, which relates to the probability of neuropsychological sequelae to the brain RT dose. This pooling of data suggests a dose response effect with greater morbidity seen with increasing cranial RT dose. There has only been one study that attempted to examine this dose effect in the context of a randomised control trial. Mulhern examined the neuropsychological functioning of survivors of children with medulloblastoma entered into the POG 8631/CCG 923 study described below 23. This showed that children treated with 23.4 Gy CSRT experience less neuropsychological toxicity than those treated with 36 Gy CSRT. However, the number of patients studied was small, the individual patients IQ changes varied considerably and the results of this cross sectional analysis were not confirmed on a longitudinal basis.

In the recently completed CCG 9892 study, the neuropsychological effect of 23.4 Gy CSRT was reported to be a decline of 4.3 Full Scale IQ points per year. The median interval between radiotherapy and the patient's most recent evaluation in that study was 2.5 years. The declines in IQ were reported to be relatively more marked in females, children with higher baseline scores and children aged less than 7 years. The authors considered that their findings were suggestive of some degree of intellectual preservation compared to the effect of conventionally dosed radiotherapy but also stated that the estimated IQ drop of 20.8 points in their younger group did not clearly support an advantage to these patients for the reduced radiotherapy regimen.

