### 7. STUDY ENTRY and RANDOMISATION

Randomisation will be stratified for each country or group of countries and will be undertaken separately in each national data centre i.e. CRCTU, HIT, Italy, Nordic countries and SFOP. Further stratification will be by the presence or absence of residual tumour after surgery and by sex. Blocked randomisation will be balanced, using tables of random numbers, in order to ensure that there are equal numbers of patients in each treatment group (50% in each arm) at the end of the inclusion period. Block size may vary from one country to another, but will be a function of the number of patients to be included in the trial.

- > Randomisation is Mandatory for Entry into the Study.
- > Randomisation must be performed within 28 days following surgery.
- ➤ Registration will only be permitted following confirmation of LREC approval to be sent to the CRCTU.
- > Registration and Randomisation into the study will be conducted at the CRCTU by Faxed Registration Form:

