### HIT Group patients:

- 1. Null hypothesis: The EFS, PFS and OS between patients with HFRT is not different from the EFS, PFS and OS in the historical similar group in the HIT-91 study with standard RT without reduction of the craniospinal dose. These hypotheses should be tested with a two sided log-rank test.
- 2. Null hypothesis: The 4 year EFS-, PFS- and OS-survival rate in patients with standard RT is smaller than the 10% reduced 4 year EFS-, PFS- and OS-survival rate in the historical similar group in the HIT-91 study with standard RT. These hypotheses should be tested with a one sided log-rank-test.
- 3. Null hypothesis: There is no difference in the intelligence quotient in patients with HFRT compared to patients with standard RT. This hypothesis should be tested with a two sided Wilcoxon test for unrelated samples.
- 4. Null hypothesis: There is no difference in the grade of leucoencephalopathy in patients with HFRT compared to patients with standard RT. This hypothesis should be tested with a two sided Wilcoxon test for unrelated samples.
- 5. The importance of the prognostic factors for No. 5 of the secondary questions for HIT Group patients listed in section 13.3 on EFS, PFS and OS will be estimated with Cox-regression analysis.

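### The HIT-group IQ comparison is fixed as an unadjusted rank test, giving up precision that age and the randomisation strata would supply

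*Protocol*

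**What the plan says.** Section 13.3 lists an IQ difference between the arms among the additional secondary questions for HIT Group patients. Section 13.8, HIT Group patients, item 3, gives the null hypothesis as "There is no difference in the intelligence quotient in patients with HFRT compared to patients with standard RT" and fixes the method: "This hypothesis should be tested with a two sided Wilcoxon test for unrelated samples". It names no covariate, stratum or effect estimate. Section 13.8 also states that p-values for the secondary questions are explorative.

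On what drives IQ loss, section 4.4.1 says that losses of up to 30 points or more are "most predominant in young children, particularly those less than seven or eight years of age". On one cited study of 23.4 Gy craniospinal radiotherapy, the dose of the standard arm here, it adds: "The declines in IQ were reported to be relatively more marked in females, children with higher baseline scores and children aged less than 7 years". That study's report is also cited as concluding that "the estimated IQ drop of 20.8 points in their younger group did not clearly support an advantage" of the reduced dose for those patients.

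Section 13.1 gives the age range as 4 to 21 years. Section 7 stratifies randomisation by country or group of countries and continues: "Further stratification will be by the presence or absence of residual tumour after surgery and by sex". Age is not a stratum. For the definition of IQ, section 13.4 refers to Appendix 5 of the HIT 2000 protocol, which is not shown.

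**The concern.** The protocol names a major source of IQ variation, age at irradiation, and then fixes a test that uses none of it. Age is balanced by chance only and is not in the analysis. Sex is balanced by design, and the analysis ignores that.

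The plan treats comparable outcomes differently. For the same HIT patients, age and sex are listed in section 13.3 as prognostic factors for the survival endpoints and go into Cox regression (section 13.8, HIT item 5). Section 13.12 foresees multiple regression for other continuous late-effect outcomes, but it covers HUI, SDQ, endocrine and audiological data, not IQ.

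At stake is how sharply the cognitive question is answered in a limited number of patients. IQ is asked about only in the HIT Group, and section 4.7.3.1 says quality of survival has gained importance because emerging data suggest no significant difference in event-free survival.

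**Working it through.** **No stated figure to reproduce.** The protocol gives no sample size, standard deviation, effect size or power for IQ. What follows is illustration, and every input that is not from the protocol is marked as assumed.

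**Step 1: gain from adjustment.** If covariates explain a share R² of the IQ variance, the residual SD falls by the factor √(1−R²). A difference with 80% power at two-sided 0.05 (assumed) corresponds to 2.80 standard errors, so

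adjusted power = Φ(2.80/√(1−R²) − 1.96), and the equivalent gain in patients = 1/(1−R²) − 1.

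| R² (assumed) | Calculation | Adjusted power | Equivalent extra patients |
|---|---|---|---|
| 0.05 | Φ(2.87 − 1.96) | 82% | 5% |
| 0.10 | Φ(2.95 − 1.96) | 84% | 11% |
| 0.20 | Φ(3.13 − 1.96) | 88% | 25% |

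**Step 2: is 5-20% a sensible range?** Take a residual SD of 15, 40% of patients under 7, and a mean gap between younger and older children of 8, 12 or 16 points (all assumed). Then R² = gap² × 0.4 × 0.6 / (gap² × 0.4 × 0.6 + 225):

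- gap 8: 15.4/240.4 = 6%
- gap 12: 34.6/259.6 = 13%
- gap 16: 61.4/286.4 = 21%

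The protocol gives 20.8 points as the drop in the younger group but no figure for the older group, so the gap itself cannot be read from it.

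**Step 3: illustration in absolute terms.**

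- Number of HIT patients: about 85 randomised by July 2003 (introduction). Alternatively, 33.6 per year × 5 years = 168, if the early rate in section 13.10 continued for HIT alone (assumed).
- Evaluable per arm, borrowing 75% event-free survival and 10% loss from section 13.12: 85 × 0.75 × 0.90 / 2 ≈ 29, and 168 × 0.75 × 0.90 / 2 ≈ 57.
- Difference between arms, interpolated from the mean IQs in section 4.4.1 (84.5, 76.9 and 63.7 at 0, 25 and 35 Gy) for the late-effect equivalent doses of 28.42 Gy (Table 1) and 23.4 Gy. With the 25-35 Gy slope throughout: (76.9 − 63.7)/10 × 5.02 = 6.6 points. Piecewise: 1.6 × (84.5 − 76.9)/25 + 3.42 × 1.32 = 5.0 points.
- Power = Φ(difference/(SD × √(2/n)) − 1.96), with SD 15 (assumed). For the Wilcoxon test n is multiplied by 0.955; for the adjusted model the SD is multiplied by √(1−R²).

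| Per arm | Difference | Wilcoxon | Adjusted, R² 0.1 | Adjusted, R² 0.2 |
|---|---|---|---|---|
| 57 | 6.6 | 0.63 | 0.69 | 0.75 |
| 57 | 5.0 | 0.41 | 0.46 | 0.51 |
| 29 | 6.6 | 0.37 | 0.42 | 0.46 |
| 29 | 5.0 | 0.23 | 0.26 | 0.29 |

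**Step 4: validity.** In simulation (3,000 runs per setting, 29 and 57 per arm, R² of 0.1, 0.3 and 0.5) the type I error was 0.043 to 0.055 for both analyses. The unadjusted test is not wrong, only less efficient.

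**The case against.** The strongest reply is that nothing here is an error. The arms are randomised, the Wilcoxon test holds its level, the p-value is declared explorative, and the question belongs to one national group. The primary log-rank test is also written without covariates, so unadjusted testing is the protocol's general style. HUI cognition is compared in all groups, with regression to follow. An estimate in IQ points could accompany the Wilcoxon test as a Hodges-Lehmann shift, and such reporting is commonly left to the analysis plan. All of this stands. It limits the point to precision and keeps it minor.

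Four stronger readings are tempting, and the documents do not support them:

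- **That the test hides or biases the cognitive effect.** It does not. What is lost is power and precision.
- **That age, sex and baseline score are all strong determinants.** Only age has that support. For sex and baseline score the text says no more than relatively more marked, from one cited study of decline, whereas item 3 as worded compares IQ.
- **That every useful covariate is already recorded.** Whether a pre-radiotherapy IQ exists cannot be seen, because the definition sits in HIT 2000 Appendix 5.
- **That the interval from radiotherapy to testing should be adjusted for, with a larger gain.** That interval arises after randomisation. If testing is at fixed times, as for the protocol's other late-effect assessments, it would explain almost nothing.

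**Conclusion.** The point holds as a minor loss of efficiency. The protocol itself fixes an unadjusted test, so this is not detail left to an analysis plan, and its own rationale identifies age as the main source of avoidable variation. Age and the two strata are available for every randomised patient.

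The gain is modest and uncertain: from 80% to about 82-88% power if age and the strata explain 5-20% of IQ variance. That rests on an assumed SD, age gap and share of children under 7, none of which the protocol gives. No confirmatory conclusion of the trial depends on it.

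**What to change.** Before IQ is examined by arm, amend section 13.8, HIT Group patients, item 3, so that:

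- The main comparison is a linear model of IQ on arm, adjusted for age at radiotherapy (continuous), sex and residual tumour.
- Pre-radiotherapy IQ is added only if HIT 2000 measured it in essentially all patients; otherwise patients would be lost or covariates imputed in a small group.
- The result is reported as the adjusted mean difference with a 95% CI.
- A Wilcoxon test stratified by sex and age group (van Elteren) is kept as the robustness check.

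The cost is an amendment to the analysis wording, with no new patients, visits or measurements. The downside is a linear-model assumption, which the stratified rank test covers. Timing matters, because this version dates from July 2010, when event-free survival by arm was already emerging. If IQ by arm has been seen, the adjusted model should be reported as supplementary, with the Wilcoxon test as specified.

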### 13.9 Per protocol analysis

A per protocol analysis will also be carried out to study stability of results, but confirmatory conclusions will depend on the Intention to Treat analysis.

[figure not shown]
The per protocol analysis will exclude patients who have been randomised but who do not meet the eligibility criteria e.g. age, histology, staging, other malignant tumour disease etc. In addition, this analysis will exclude patients who do not meet eligibility criteria after central review (pathological, radiological and radiotherapy review) and patients who are not reviewed. Patients will also be excluded from per protocol analysis for the following reasons: patients who, do not receive any treatment at all, start RT more than 40 days after definitive surgery, do not meet RT quality assurance because of major deviations on RT treatment chart, receive less than 75% of the intended RT arm and thereafter are switched to the other arm, receive less than 90% of intended RT dose and patients who receive less than 4 cycles of chemotherapy with less than 80% of doses applied in each cycle. In the per

protocol analysis, if a patient is allocated to one arm and receives the other arm as treatment, analysis will be according to the treatment actually given.

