# QC review of posterior fossa and tumour bed

QC review of posterior fossa and tumour bed target volumes will be organised on a national level.

- Radiotherapy QC of the posterior fossa component is not mandatory unless the patient experiences a posterior fossa relapse (see below) in which case a retrospective QC review is mandatory.
- Some National groups may, however, wish to conduct prospective QC of posterior fossa radiotherapy. If such prospective QC is undertaken, then the National Radiotherapy QC panel will be responsible for determining the criteria by which posterior fossa treatment techniques are evaluated.
- For some National Groups Radiotherapy QC of the posterior fossa component will be organised on the basis of national educational 'workshops'.
- All patients who relapse within the posterior fossa either alone or in combination with other sites will undergo a separate radiotherapy QC. Centers will be requested to provide the documentation of their posterior fossa and/or tumor bed boost together with the diagnostic imaging at diagnosis and relapse. The radiotherapy QC panel, in collaboration with appropriate neuro-radiologists if indicated, will determine the exact site of relapse as a function of irradiation volume.

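### Section 13.9's RT-dose and chemotherapy-cycle thresholds drop patients from the per-protocol set because of the EFS event being analysed

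*Protocol*

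**What the plan says.** Section 13.9 gives the per-protocol analysis a supporting role: "A per protocol analysis will also be carried out to study stability of results, but confirmatory conclusions will depend on the Intention to Treat analysis".

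It then lists the exclusions. Three kinds matter here:

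- **RT dose:** patients who "receive less than 90% of intended RT dose".
- **Chemotherapy:** "patients who receive less than 4 cycles of chemotherapy with less than 80% of doses applied in each cycle".
- **RT quality and review:** patients who "do not meet RT quality assurance because of major deviations on RT treatment chart", and those found ineligible at central review ("pathological, radiological and radiotherapy review) and patients who are not reviewed").

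None of these rules says what happens to a patient whose treatment ended because an EFS event occurred, and no landmark is set. Section 13.4 starts EFS on the day of surgery and counts relapse, progression, death from any cause and second tumours as events.

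Section 8.8 makes craniospinal RT quality control mandatory, to be done for every patient within a year of diagnosis. For the posterior fossa, by contrast, "Radiotherapy QC of the posterior fossa component is not mandatory unless the patient experiences a posterior fossa relapse".

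**The concern.** A patient who relapses or dies before the fourth course cannot receive four courses. Excluding that patient for too little chemotherapy therefore excludes the patient for having had the event. The remaining patients are event-free, by construction, up to roughly the time the threshold can be met, although their EFS clock has been running since surgery. The RT-dose rule works the same way for an event during radiotherapy.

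The analysis exists to show whether the intention-to-treat result is stable. If its EFS levels and absolute difference move because early failures were deleted, a reader comparing the two analyses cannot tell how much of the gap reflects adherence. The four-cycle phrase can also be read in two ways, and these remove different numbers of patients.

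**Working it through.** **1. Reproduce the plan's own design figure (section 13.10).** Constant hazards, 3-year EFS 70% and 85%:

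- λ = −ln(S)/3, so λ(standard) = 0.1189 and λ(HFRT) = 0.0542 per year; HR = 0.456.
- Accrual: 33.6 × 2.8 + 102.7 × 2.2 = 320.0; with 67.3 in the second period, 242.1.
- Recruitment stops at 5 years and the study ends at 7, with no losses: about 87 expected events for n = 320.
- Two-sided α = 0.04: power = Φ(√87/2 × |ln 0.456| − 2.054) ≈ 0.947. Simulated log-rank power is about 0.94.
- At 70% against 84%, simulated power is 0.899 (n = 320) and 0.813 (n = 242). This matches the statement that the 90% curve for 320 and the 80% curve for 242 almost coincide. The design assumptions are reproduced and not in dispute.

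**2. When cycle 4 starts, in days from surgery.** Inputs: RT start by day 40 (section 8.1); 30 daily fractions at 5 per week, or 68 at 10 per week (section 8.7.4); chemotherapy 6 weeks after RT and 42-day courses (section 10.1).

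| | Surgery to RT | RT | Gap | Three courses | Cycle 4 starts |
|---|---|---|---|---|---|
| Standard | 40 | 42 | 42 | 126 | day 250 |
| HFRT | 40 | 47.6 | 42 | 126 | day 255.6 |

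With the preferred 28 days to RT, these become days 238 and 243.6.

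**3. Patients removed, reading the rule as fewer than four adequate cycles.** f = 1 − exp(−λt), with 160 per arm:

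- Standard: 1 − exp(−0.1189 × 250/365.25) = 0.078, or 12.5 patients.
- HFRT: 1 − exp(−0.0542 × 255.6/365.25) = 0.037, or 6.0 patients.
- Together about 18.5 of 87 events. With 28 days to RT: 11.9 and 5.7.

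**4. Effect on EFS levels.** Per-protocol 3-year EFS = S/(1 − f):

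- Standard: 0.70/0.922 = 75.9%.
- HFRT: 0.85/0.963 = 88.3%.
- Difference: 12.4 points instead of 15. With 28 days to RT: 75.6% and 88.1%, difference 12.5.

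**5. Effect on the comparison.** Simulation under the section 13.10 assumptions, deleting every patient with an event before cycle 4:

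| | All patients | Per protocol |
|---|---|---|
| Events | 87 | about 69 |
| Estimated HR | 0.47 | 0.46 |
| Power | about 0.94 | 0.87 |
| Rejection with no true effect | about 0.04 | about 0.04 |

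**6. Literal, joint reading.** If a patient is excluded only when there are fewer than four cycles and also less than 80% of dose in each, a child who relapses after two full-dose cycles stays in. A patient with an event before cycle 1 has had no chemotherapy and still falls out. Cycle 1 starts at 40 + 42 + 42 = day 124 (standard) and 40 + 47.6 + 42 = day 129.6 (HFRT):

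- Standard: 1 − exp(−0.1189 × 124/365.25) = 0.040, or about 6 patients.
- HFRT: 1 − exp(−0.0542 × 129.6/365.25) = 0.019, or about 3 patients.
- Per-protocol 3-year EFS: about 73% and 87%.

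**The case against.** The strongest reply is that little is at stake. Confirmatory conclusions rest on intention to treat; no alpha, sample size or primary claim depends on the per-protocol set. The hazard ratio and type I error barely move, so the treatment comparison is not shown to be biased. On the literal wording of the chemotherapy rule, only the earliest events are lost. All of this stands, and it sets the severity. It does not remove the defect, because even the narrowest reading excludes some patients on account of their outcome.

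Three stronger readings are tempting and are not supported.

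- **A reader might infer that relapse-triggered posterior-fossa review feeds the RT-quality exclusion,** so that only patients with events are found to have deviations. Section 8.8 mentions treatment charts and defines major deviations only under craniospinal QC, which covers all patients. The stated purpose of the relapse-triggered review is different: the panel "will determine the exact site of relapse as a function of irradiation volume". No text links it to the per-protocol set, though none rules it out.
- **A reader might go on to infer a distorted hazard ratio.** The protocol gives no posterior-fossa deviation rates, so any such figure is assumed. Removing an equal 5–20% of events in both arms leaves the design HR at 0.45–0.46. Only an assumed imbalance moves it: removing 5% in one arm and 20% in the other gives an HR of 0.87 or 1.15 when there is no true effect, depending on direction.
- **A reader might object to patients who received the other arm being kept,** since "analysis will be according to the treatment actually given". Section 13.9 states this openly. Excluding or re-labelling them is a choice between two non-randomised comparisons, not an error.

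**Conclusion.** The point holds as a low-severity defect in a supportive analysis. Section 13.9's dose and cycle thresholds select on the endpoint because they have no exemption for treatment stopped by the EFS event.

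On the reading of fewer than four adequate cycles, about 12 to 13 standard and 6 HFRT patients are lost. Three-year EFS is overstated by about 6 and 3 points, the difference shrinks from 15 to about 12.4 points, and power falls from about 0.94 to 0.87. On the joint reading, about 6 and 3 patients are lost.

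These sizes assume section 13.10's constant hazards, treatment on the planned timetable and exclusion of every patient whose event precedes the relevant cycle. If early events were rarer than a constant hazard implies, the numbers would be smaller. The stability of the hazard ratio depends on proportional hazards.

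**What to change.** Reword section 13.9 in three places:

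1. Count a patient as per protocol if RT and chemotherapy followed the protocol up to the EFS event. Apply the RT-dose, cycle and 80% thresholds only to treatment that was due before that event.
2. State whether the four-cycle and 80% conditions must both be met for exclusion or whether either is enough.
3. State that the RT-quality exclusion, and the not-reviewed exclusion as it concerns radiotherapy, refer only to the craniospinal QC done in all patients regardless of outcome, and not to the posterior-fossa review triggered by relapse. This is a safeguard, because the present text leaves the matter open.

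The cost is a text change, with no new data. The downside is that some patients who received little treatment before an early event stay in the per-protocol set.
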